#### Neonatal:

- Grade  $\geq 3$  AEs
- Congenital defects

- HIV infections
- Pneumonia or IPD

2. To compare the immunogenicity of PCV-10 with PPV-23 vaccines in HIV-infected pregnant women on HAART.
  - Outcome measure:
    - Raw values and fold change in ELISA-measured IgG PNC antibody concentrations from baseline to week 4 in Step 1 to  $\geq 1$  serotype. Serotypes measured by ELISA are: 1, 4, 5, 6B, 7F, 14, 23F and 33F.
3. To compare the level of Pneumococcal (PNC) antibodies at 8 weeks of life in infants born to mothers who received PCV-10 or PPV-23 vaccines.
  - Outcome measures:
    - ELISA-measured IgG PNC antibody levels  $\geq 0.35\text{ug/mL}$  at 8 weeks of age for  $\geq 1$  serotype from those listed above.

Secondary objectives and outcome measures:

1. To compare the level of transplacentally transferred vaccine-serotype PNC antibodies in infants born to mothers who received PCV-10 or PPV-23 versus placebo.
  - Outcome measure: Average ratio of infant/mother ELISA-measured IgG PNC antibody levels across the serotypes listed above, measured at birth/delivery
2. To compare the immunogenicity of PCV-10 and PPV-23 vaccines with placebo in HIV-infected pregnant women on HAART.
  - Outcome measure: ELISA-measured IgG PNC antibody concentrations at week 4 in Step 1, in all treatment groups
3. To compare the persistence of vaccine-serotype PNC anti-capsular antibodies for up to 24 weeks after delivery in HIV-infected women vaccinated with PCV-10, PPV-23 or placebo.
  - Outcome measure: ELISA-measured IgG PNC antibody concentrations at labor&delivery and week 24 post-delivery in Step 1, in all treatment groups
4. To compare maternal antibody responses to PPV-23 or PCV-10 administered during pregnancy with responses to PPV-23 or PCV-10 administered 24 weeks postpartum.
  - Outcome measure: ELISA-measured IgG PNC antibody concentrations at week 4 in

Step 1 and at week 4 in Step 2, in the women who received PPV-23 or PCV-10

5. To evaluate the effect of the following factors on the magnitude and persistence of the maternal antibody responses to PCV-10 and PPV-23: maternal age, ethnicity, cluster of differentiation 4 (CD4), cluster of differentiation 8 (CD8), plasma HIV RNA and gestational age at immunization.
  - Outcome measure: ELISA-measured IgG PNC antibody concentrations at week 4 in Step 1, in the women who received PPV-23 or PCV-10, and the following variables (measured at week 0):
    - maternal age,
    - ethnicity,

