    - cluster of differentiation 4 (CD4),
    - cluster of differentiation 8 (CD8),
    - plasma HIV RNA and
    - gestational age.
6. To assess potential interference of maternal antibodies with infant vaccine-serotype PNC anti-capsular antibody responses after the first 2 doses of PCV-10 and determine if interference of maternal antibodies differs in PCV-10 from PPV-23 and from placebo recipients.
  - Outcome measure: ELISA-measured IgG PNC antibody concentrations at weeks 16 and 24 in infants

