#### Infant Schedule:

Study visits for infants were conducted at birth (with a window of +7 days), week 8, which should be  $\leq 7$  days before the 1st dose of PCV-10 (with a window of +14 days), week 16, which should be  $\leq 7$  days before the 2nd dose of PCV-10 (with a window of  $\pm 28$  days), week 24, which

should be  $\geq$  28 days after the 2nd dose of PCV-10 (with a window of 28 days), or for Invasive Pneumococcal Disease (IPD).

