### Infants:

This is an as-treated analysis including only the infants born to women who have been vaccinated and those who have received the PCV-10 vaccination prior to the week 8 study visit.

Summaries will include the proportion (%) and 95% CI of infants born to mothers who received PCV-10 or PPV-23 vaccines who had ELISA-measured IgG PNC antibody levels  $\geq 0.35\mu\text{g/mL}$  at 8 weeks of age for  $\geq 1$  serotype listed above. The difference in proportions between the two groups will be assessed using a Chi-Square test.

In the case of twins, one child will be chosen at random for the primary immunogenicity analysis. Sensitivity analyses will repeat these summaries in the event that twins are enrolled in the study, re-doing the analysis using the other sibling.

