## 5.4 Secondary Objectives

Summaries will include:

- i) means (or medians if data are not normally distributed) and 95% CI of mean ratio of infant/mother ELISA-measured IgG PNC antibody levels across the serotypes listed above, measured at birth/delivery;
- ii) Summary table with proportion (%) and 95% CI of women in the each treatment group who had a  $\geq$ two-fold increase to each serotypes in ELISA-measured IgG PNC antibody concentrations from baseline to week 4 after immunization in Step 1;
- iii) Summary table with proportion (%) and 95% CI of women by treatment arm who had ELISA-measured IgG PNC antibody levels  $\geq 0.35\text{ug/mL}$  at week 4 after immunization in Step 1, at labor&delivery, and at week 24 post-delivery in Step 1 to  $\geq 1$  of the serotypes listed above;
- iv) Summary table with proportion (%) and 95% CI of women who had a two-fold increase to  $\geq 1$  serotype in ELISA-measured IgG PNC antibody concentrations from baseline to week 4 after immunization in Step 1 vs the women who achieved this from entry to Step 2 until week 4 post immunization in Step 2 (for each of the two vaccines). The analyses will exclude the women who delivered prior to week 4 in Step 1;
- v) Correlations between ELISA-measured IgG PNC antibody concentrations at weeks 4 in Step 1, in the women who received PPV-23 or PCV-10, and the following variables (measured at week 0): maternal age, ethnicity, cluster of differentiation 4 (CD4) count, cluster of differentiation 8 (CD8) count, plasma HIV RNA and gestational age;
- vi) Summary table with proportion (%) and 95% CI of infants born to mothers who received PCV-10 or PPV-23 vaccines who had ELISA-measured IgG PNC antibody levels  $\geq 0.35\text{ug/mL}$  at 16 and 24 weeks of age for  $\geq 1$  serotypes listed above;
- vii) Summary table with mean (95% CI) number of serotypes with levels  $\geq 0.35\text{ug/mL}$  at weeks 16 and 24 of age in study infants.

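### Two secondary objectives are only half answered: objective 5 never relates the factors to antibody persistence, and objective 1 plans an infant/mother ratio instead of infant antibody level versus placebo

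*SAP*

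**What the plan says.** **Objective 5.** Section 3.2 sets out to study the effect of the listed factors on "the magnitude and persistence of the maternal antibody responses to PCV-10 and PPV-23: maternal age, ethnicity", followed by CD4, CD8, plasma HIV RNA and gestational age at immunization. The outcome measure beneath it is limited to "concentrations at week 4 in Step 1, in the women who received PPV-23 or PCV-10, and the following variables (measured at week 0"). Section 5.4 item v repeats that limit: "Correlations between ELISA-measured IgG PNC antibody concentrations at weeks 4 in Step 1, in the women who received PPV-23 or PCV-10". Delivery and week 24 post-delivery, which objective 3 uses to define persistence, enter section 5.4 only in item iii, as proportions by treatment arm.

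**Objective 1.** Section 3.2 states: "To compare the level of transplacentally transferred vaccine-serotype PNC antibodies in infants born to mothers who received PCV-10 or PPV-23 versus placebo". The outcome measure is "Average ratio of infant/mother ELISA-measured IgG PNC antibody levels across the serotypes listed above, measured at birth/delivery". Item i of section 5.4 summarises that ratio and names neither the arms nor a contrast with placebo.

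**Other infant analyses.** The week-8 analysis in section 5.3 covers the "proportion (%) and 95% CI of infants born to mothers who received PCV-10 or PPV-23 vaccines", with a chi-square test between those two groups. Item vi of section 5.4 names the same two groups. The outcome measure of objective 6 is "ELISA-measured IgG PNC antibody concentrations at weeks 16 and 24 in infants", and item vii summarises the number of serotypes above the threshold at those two ages.

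**The concern.** In both cases the objective asks a question that its outcome measure and analysis cannot answer.

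For objective 5, a factor that acts only on what happens after week 4 leaves no trace in a week-4 correlation. The persistence half of the objective would go unreported although the later samples are assayed.

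For objective 1, a ratio of infant to maternal antibody describes how efficiently antibody crosses the placenta. It does not say how much the infant has. If transfer is equal in all arms, the ratio shows no difference however far apart the infant levels are. If transfer is less efficient after vaccination, the ratio falls even where vaccinated mothers' infants have more antibody. Either way the report does not say whether maternal vaccination raised infant antibody at birth above placebo.

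A smaller point: item v lists ethnicity under correlations with no method named. That is unsuitable if ethnicity has three or more unordered categories.

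**Working it through.** The SAP gives no power or effect size here, so there is no stated figure to reproduce. The finding rests on comparing the SAP's sections; the arithmetic only shows what is at stake.

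**1. Does anything else fill the gap?**

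| Place in SAP | Supplies | Does not supply |
|---|---|---|
| 5.4 item v | Factors against week-4 IgG | Delivery or week 24 post-delivery |
| 5.4 item iii | Delivery and week-24 proportions by arm | Any factor |
| 5.4 item i | Infant/mother ratio at birth | Infant level; a stated placebo contrast |
| 5.3, infants | Infant level at week 8 | Placebo arm |
| 5.4 item vi | Infant level at weeks 16 and 24 | Placebo arm; a time before infant PCV-10 |
| 5.4 item vii | All study infants, weeks 16 and 24 | A time before infant PCV-10 |
| 5, general chi-square sentence | Vaccinated versus placebo response rates | Any infant endpoint or time point |

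Section 5.1 places the first infant dose just after the week-8 visit, so weeks 16 and 24 no longer show transferred antibody alone.

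**2. Ratio against level**

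Infant fold difference = maternal fold difference × relative transfer (assumed values):
- Equal transfer: 2 × 1.0 = 2. Infants differ two-fold; the ratios are identical.
- Reduced transfer: 2 × 0.8 = 1.6. Infants are 1.6-fold higher; the ratio is 20% lower.

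**3. Power for objective 1**

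Inputs: 100 evaluable pairs per arm (section 3.1) and two-sided 0.05 (section 5). All SDs are assumed. Method: two-sample t test on the log scale, with 95% CI = fold ÷ and × exp(1.972 × SD × √(2/100)).

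Infant IgG:

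| SD of ln IgG | CI factor | Power, 2-fold | CI, 2-fold | Power, 1.6-fold | CI, 1.6-fold |
|---|---|---|---|---|---|
| 1.0 | 1.32 | 99.8% | 1.51–2.64 | 91% | 1.21–2.11 |
| 1.2 | 1.40 | 98% | 1.43–2.79 | 79% | 1.14–2.24 |
| 1.4 | 1.48 | 94% | 1.35–2.96 | 66% | 1.08–2.36 |

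Infant/mother ratio, chance of p < 0.05:

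| SD of ln ratio | Relative transfer 1.0 | 0.9 | 0.8 |
|---|---|---|---|
| 0.4 | 5% | 46% | 98% |
| 0.5 | 5% | 32% | 88% |
| 0.6 | 5% | 24% | 74% |

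At relative transfer 0.8 the ratio is likely to be significant, in the direction opposite to the infant level.

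**4. Power for objective 5**

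A factor acting only after week 4 has a week-4 correlation of 0 by construction. Suppose its week-24 partial correlation r is 0.2 to 0.3 (assumed), in a model with arm and time since vaccination. Then power = Φ(atanh(r) × √(n − 2 − 3) − 1.96).

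| r | n = 200 (both vaccine arms) | n = 160 (assumed 20% loss) |
|---|---|---|
| 0.2 | atanh(0.2) × √195 = 2.83; 81% | 2.52; 71% |
| 0.3 | 4.32; 99% | 3.85; 97% |

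**5. Why gestational age at immunization needs separate handling**

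Vaccination runs from 14w0d to 32w6d (section 3.1), a range of 18.86 weeks. If uniform (assumed), its SD is 18.86/√12 = 5.4 weeks. With an assumed SD of gestational age at delivery of 1.5 to 2.5 weeks, its correlation with time from vaccination to delivery is −5.4/√(5.4² + 1.5²) = −0.96 to −5.4/√(5.4² + 2.5²) = −0.91. Adjusting this factor for elapsed time would remove most of its own variation.

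**The case against.** The strongest objection concerns objective 1. The team deliberately paired it with a ratio, so the level transferred may mean the extent of transfer, and the fault would then be loose wording. This reading is possible, but the objective speaks of level in infants versus placebo, which a ratio does not measure. If transfer efficiency was meant, the objective should say so.

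For objective 5, regressing later antibody levels on the factors does not isolate decline: a factor that affects only the peak would also show up at week 24. That is correct and limits interpretation. But levels at delivery and week 24 are the SAP's own persistence measure under objective 3, and they would pick up a factor acting only after week 4, which week 4 cannot.

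The separate Analysis Implementation Plan might hold more detail. Section 1 gives it table outlines and coding descriptions, while the outcome measures are fixed in the SAP.

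It is also fair that almost all inputs are assumed, that n = 160 takes a loss off a number already described as evaluable, and that these are secondary objectives. The numbers show feasibility, not the likely size of the loss.

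**Conclusion.** The concern holds. Followed as written, the SAP leaves the persistence half of objective 5 unanswered. For objective 1 it can report no difference, or a difference in the opposite direction, while infant levels are higher after maternal vaccination. The mismatch is in the SAP's own text and depends on no assumption. The illustrated sizes rest on assumed SDs, fold differences, relative transfer, correlations and loss; only the 100 pairs per arm and the 0.05 level are SAP figures. The primary analyses are unaffected. The change should be made.

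**What to change.** Amend sections 3.2 and 5.4 together.

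- **Objective 5, item v.** Keep week 4. Add regressions of log IgG on each factor at delivery (in women who deliver after the week-4 visit) and at week 24 post-delivery, with vaccine arm in the model and ethnicity as categorical. Choose one antibody summary in advance: per serotype, or mean log IgG across serotypes. Adjust for time since vaccination for every factor except gestational age at immunization, and report that association as including elapsed time.
- **Objective 1, item i.** Add infant log IgG at birth by maternal arm, with the geometric mean ratio of each vaccine to placebo and its 95% CI. Keep the infant/mother ratio, stated by arm, as the measure of transfer efficiency.
- **Status.** Label the additions post hoc if outcome data have been seen, as section 5 requires, and align the protocol and registry outcome lists where needed.
- **Alternative.** Reword the objectives to cover only week-4 factors and transfer efficiency.

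No new samples or assays are needed: item i already requires infant birth IgG, and item iii already requires maternal IgG at delivery and week 24. The cost is wording, a few models and possibly a protocol and registry update. Section 5 makes no multiplicity adjustment, so the additions to objective 5 bring 6 factors × 2 time points = 12 tests on mean log IgG (12 × 0.05 = 0.6 false positives expected if no effect is real). Done for each of the 8 serotypes, they bring 96 tests (4.8 expected).

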## **4 Definitions**

### **4.1 Baseline**

Study Day 0 is defined as the vaccination date. The values used for baseline summaries will be the last evaluation on or before the vaccination date.

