## 5 Statistical Methods

Baseline characteristics will be summarized by treatment group but with no statistical comparisons comparing arms.

Statistical tests will not be adjusted for interim monitoring or multiple comparisons. The Chi-square tests will be used to compare rates of response following vaccination between the vaccinated groups and placebo group. The statistical tests will be two-sided with a nominal significance level of 0.05. Categorical data will be summarized using N (%) and 90% or 95% confidence intervals (CIs), and continuous data using N, min, Q1, median, Q3, max, and mean (STD) (when appropriate) and 95% CI.

Any modifications to outcome measures after the team has seen data collected after entry will be identified as *post hoc* in the analysis report.

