## 5.3 Immunogenicity Primary Objectives

### Maternal:

This is an as-treated analysis including only the women who have been vaccinated.

Summaries will include: (i) the proportion (%) and 95% CI of women vaccinated with PCV-10 or with PPV-23 vaccines who had a  $\geq$ two-fold increase to  $\geq 1$  serotype in ELISA-measured IgG PNC antibody concentrations from baseline to 28 days after immunization in Step 1 (as measured at study week 4). The difference in proportions between the vaccinated groups will be assessed using a Chi-Square test; (ii) the proportion (%) and 95% CI of women vaccinated with PCV-10 or with PPV-23 vaccines who had ELISA-measured IgG PNC antibody levels  $\geq 0.35\mu\text{g/mL}$  at week 4 after immunization in Step 1 to  $\geq 1$  of the serotypes listed above.

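### Secondary objective 5 asks what affects the antibody response, but item v relates the factors only to the absolute week 4 level and leaves out baseline IgG, so the two sources of a high level cannot be told apart

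*SAP*

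**What the plan says.** Secondary objective 5 in SAP section 3.2 is "To evaluate the effect of the following factors on the magnitude and persistence of the maternal antibody responses to PCV-10 and PPV-23". The outcome measure listed under it is "ELISA-measured IgG PNC antibody concentrations at week 4 in Step 1, in the women who received PPV-23 or PCV-10, and the following variables", followed by six variables taken at week 0. Section 5.4 item v carries this out as "Correlations between ELISA-measured IgG PNC antibody concentrations at weeks 4 in Step 1, in the women who received PPV-23 or PCV-10", on the one side, and "maternal age, ethnicity, cluster of differentiation 4 (CD4) count, cluster of differentiation 8 (CD8) count, plasma HIV RNA and gestational age" on the other. Neither place names baseline IgG, a change from baseline, a model or a later time point.

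Baseline IgG is available. The primary maternal outcome in section 3.2 is "Raw values and fold change in ELISA-measured IgG PNC antibody concentrations from baseline to week 4 in Step 1". Section 5.3 part (i) counts two-fold rises to at least one "serotype in ELISA-measured IgG PNC antibody concentrations from baseline to 28 days after immunization in Step 1", and items ii and iv of section 5.4 also use rises from a pre-vaccination value. Section 4.1 defines baseline: "The values used for baseline summaries will be the last evaluation on or before the vaccination date".

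Section 5 sets tests as "two-sided with a nominal significance level of 0.05" and does not adjust for multiple comparisons. Section 3.1 plans at least 100 evaluable pairs per arm.

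**The concern.** On the log scale, a week 4 concentration is the pre-vaccination concentration plus the rise after vaccination. A woman can have a high week 4 level because she started high, because she responded well, or both. The objective is about response.

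The six factors are not randomised, so nothing in the design balances baseline antibody across levels of CD4, HIV RNA, age or ethnicity. If one of them tracks prior pneumococcal exposure, and so baseline IgG, it will correlate with the week 4 level even when it has no bearing on the rise. Conversely, baseline variation dilutes the correlation for a factor that does affect the rise. A reader who takes item v as the answer to objective 5 could draw the wrong conclusion about who responds to vaccination in pregnancy.

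**Working it through.** The SAP states no figure for item v, so there is none to reproduce. The check asks how far a factor with no effect on the rise could appear related to the week 4 level.

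**Inputs from the SAP.** Two-sided 0.05 (section 5). At least 100 evaluable pairs per arm (section 3.1), so 2 × 100 = 200 vaccinated women if the two vaccines are taken together and 100 for one vaccine.

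**Assumptions, not in the SAP.** *r* is the correlation of the factor with log baseline IgG: 0, 0.10 or 0.30. The SDs of log baseline (SDb) and log rise (SDr) lie between 0.3 and 0.5. The log rise is uncorrelated with log baseline and with the factor. Each correlation is tested.

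**Step 1: correlation with the week 4 level.**
c = r × SDb / √(SDb² + SDr²)
- SDb 0.3, SDr 0.5: 0.3/√0.34 = 0.514
- SDb 0.5, SDr 0.3: 0.5/√0.34 = 0.857

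So c runs from 0.154 to 0.257 at r = 0.30, from 0.051 to 0.086 at r = 0.10, and is 0 at r = 0.

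**Step 2: chance of nominal significance (Fisher z).**
z = atanh(c) × √(n − 3); P = Φ(z − 1.96) + Φ(−z − 1.96)

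| r | c | n = 200 (√197 = 14.04) | n = 100 (√97 = 9.85) |
|---|---|---|---|
| 0 | 0 | 5% | 5% |
| 0.10 | 0.051 to 0.086 | z 0.72 to 1.21; 11% to 23% | z 0.51 to 0.85; 8% to 14% |
| 0.30 | 0.154 to 0.257 | z 2.18 to 3.69; 59% to 96% | z 1.53 to 2.59; 33% to 74% |

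**Step 3: check with a different parameterisation.** Let ρ be the correlation of log baseline with log week 4 IgG, and let the factor be unrelated to week 4 given baseline. Then c = r × ρ. The simulation used 4,000 runs at n = 200.

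| r | ρ | c | Fisher z | Simulated, no baseline | Simulated, adjusted for baseline |
|---|---|---|---|---|---|
| 0 | 0.5 | 0 | 5% | 5.4% | 5.0% |
| 0.2 | 0.5 | 0.10 | 29% | 29.4% | 4.6% |
| 0.3 | 0.5 | 0.15 | 56% | 56.0% | 5.3% |
| 0.3 | 0.7 | 0.21 | 85% | 84.9% | 4.9% |

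Adjusting for log baseline restores the nominal rate in each case.

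**Step 4: would a fold rise do instead?** Under the Step 1 assumption (rise uncorrelated with baseline) it would. It would not if women with high baselines rise less. With equal SDs at both visits, the correlation of the factor with the log rise is r(ρ − 1)/√(2 − 2ρ). At r = 0.3 and ρ = 0.5 this is 0.3 × (−0.5)/1 = −0.15, nominally significant about 56% of the time at n = 200, in the opposite direction. Baseline as a covariate handles both situations.

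**The case against.** The strongest reply is that the absolute level is a declared measure of the SAP. The primary maternal outcome covers raw values as well as fold change, section 5.3 part (ii) counts women at or above 0.35 µg/mL at week 4 with no reference to baseline, and item iii does the same. Item v also follows the outcome measure written under objective 5. All of this stands. It would be wrong to infer that section 5.3 defines response only as a rise, or that item v departs from its own outcome measure. The gap lies between that outcome measure and the question the objective puts.

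A reader might infer other things that the text does not support:
- *That determinants of prior antibody will be reported as determinants of response.* This requires a factor associated with baseline IgG, and the SAP gives no such association. At r = 0 there is no distortion.
- *That false significance is built in.* Section 5.4 presents its items as summaries, and item v names no test. The percentages apply only if the correlations are tested at the general level of section 5.
- *That the two vaccines are pooled.* Naming women who received either vaccine describes who is included. Separate correlations are equally compatible with it, so the n = 200 figures are one of two readings.
- *That item v is unworkable because ethnicity is nominal.* The term correlation is loose for such a variable, but this is a minor wording point, and its coding may be set out in the Analysis Implementation Plan.

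That plan is not at hand. Section 1 assigns it table outlines and coding descriptions, so it may settle the presentation by vaccine. It does not answer the main point, because the SAP itself fixes the outcome and the list of variables without baseline IgG.

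**Conclusion.** The point holds as a limit on what item v can show: correlations with the week 4 level describe who has high antibody after vaccination, but do not by themselves show which factors affect the response. The size depends mostly on the unknown correlation of each factor with baseline IgG. Under the stated assumptions, the chance of a nominally significant result for a factor with no effect on the rise goes from the nominal 5% (no link to baseline), through 11% to 23% (0.10), to 59% to 96% (0.30) with 200 women. With 100 women the last range is 33% to 74%. These figures are per correlation, and section 5 makes no adjustment for multiplicity. The textual finding is firm; the percentages are illustration. It concerns one secondary objective and touches no primary conclusion, but the improvement is cheap and worth making.

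**What to change.** Rewrite section 5.4 item v, and the outcome measure under secondary objective 5 to match:
- For each serotype, regress log week 4 IgG on each factor, with log baseline IgG of that serotype and vaccine as covariates, or fit the model separately for PCV-10 and PPV-23. State which.
- Enter ethnicity as a categorical variable.
- Keep the raw correlations with the week 4 level, labelled as descriptive.
- Do not replace the week 4 level by an unadjusted fold rise, for the reason in Step 4 of the working.

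The cost is SAP wording and some programming. Baseline IgG is already required for the primary fold-change outcome, so no sample, visit or assay is added.

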## 3 Protocol Overview

### 3.1 Study Design

**DESIGN:** A double-blind, randomized, placebo-controlled study to evaluate the safety and immunogenicity of two pneumococcal vaccines in HIV-infected pregnant women in their second or third trimester on highly active antiretroviral therapy (HAART) and their infants.

**SAMPLE SIZE:** Approximately 345 Human Immunodeficiency Virus (HIV)-infected pregnant women and their 345 infants (690 participants), equally distributed among three treatment arms to obtain  $\geq 100$  evaluable pairs/arm (300 total pairs, or 600 total participants).

**REGIMEN:** **Step 1.** Pregnant women will be randomized between  $\geq 14$  weeks (14 weeks 0 days) to  $< 33$  weeks (32 weeks 6 days) of gestation to one of three blinded treatment arms (administered on Day 0):

- Arm 1A: pneumococcal polysaccharide 23-valent vaccine (PPV-23);
- Arm 1B: pneumococcal conjugate 10-valent vaccine (PCV-10); or
- Arm 1C: placebo.

**Step 2.** Women randomized to Arm 1C (placebo) who complete Step 1 will be screened for entry into Step 2 and will be randomized to receive PPV-23 (Arm 2A) or PCV-10 (Arm 2B) at 24 weeks after delivery. The women who received active vaccine during pregnancy (Arms 1A and 1B) will stop study at 24 weeks after delivery.

**Step 3.** Women who were initially randomized to Arm 1C and meet an exclusion criterion for Step 2 due to new pregnancy will be enrolled in Step 3 and receive open label PCV-10 at the last study visit (which coincides with Step 1 24 weeks post-delivery).

All infants will receive PCV-10 per local standard of care.

STUDY DURATION: Up to 60 weeks for women (approximately 28 weeks pre-delivery; 32 weeks post-delivery) and up to 28 weeks for infants.

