### **4.2 Analysis Populations**

Any mother participants found to be ineligible and who the study team determine should not be included in any analyses, will be included in accrual and eligibility summaries only. Protocol deviations will be summarized but should not result in any participants being excluded from analyses.

Safety population: Safety analyses will be as-treated and include all women who received study vaccination and all infants who were born alive.

Immunogenicity population: The primary immunogenicity analyses will use an as-treated approach, limited to women who received study vaccination and all infants who were born alive. In addition, the primary immunogenicity analysis in infants will be restricted to those who did not receive the PCV-10 vaccination prior to the week 8 evaluation. If more than one child is born to a pregnant woman, one child will be randomly selected to be included in the primary immunogenicity analyses.

For the immunogenicity analysis in secondary objective #6, infants who did not receive the PCV-10 vaccinations within the correct windows will be excluded. The windows are described below in section 5.1.

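### Section 5.4 item vi leaves out infants of placebo mothers, the reference group that secondary objective 6 asks to be compared

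*SAP*

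**What the plan says.** Section 3.2, secondary objective 6, sets out to assess interference with the infant response after the first two PCV-10 doses and to "determine if interference of maternal antibodies differs in PCV-10 from PPV-23 and from placebo recipients". Its outcome measure is infant IgG concentration at weeks 16 and 24, with no restriction to any maternal arm.

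Section 5.4 has two summaries at those ages:

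- Item vi, the proportion at or above 0.35 ug/mL for at least one serotype, is a "Summary table with proportion (%) and 95% CI of infants born to mothers who received PCV-10 or PPV-23 vaccines".
- Item vii, the mean number of serotypes at or above the same cut-off, is reported "at weeks 16 and 24 of age in study infants". It mentions neither arms nor a contrast.

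For the mothers, the same section uses all-arm wording: item ii refers to "women in the each treatment group who had a" two-fold rise, and item iii is a "Summary table with proportion (%) and 95% CI of women by treatment arm who had ELISA-measured IgG PNC antibody levels" above the cut-off.

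**The concern.** Interference means that infants of vaccinated mothers respond less well to their own PCV-10 than they would have done without maternal vaccination. Infants of placebo mothers are the only group in the trial that shows the response without it. A table confined to the two vaccine arms can show whether the vaccines differ from each other, but not whether either lowers the infant response. If both lower it by the same amount, the two columns agree and the table looks reassuring.

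There is also a question of prespecification. A placebo column added after the data have been seen would go beyond what item vi states and could be challenged as post hoc.

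**Working it through.** **1. Does the text of item vi meet objective 6?** The SAP gives no stated figure to reproduce on this point, so the main check is textual.

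| Contrast between maternal arms | Asked for by objective 6 | Available from item vi |
|---|---|---|
| PCV-10 vs PPV-23 | yes | yes |
| PCV-10 vs placebo | yes | no |
| PPV-23 vs placebo | yes | no |

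**2. Does anything in the design explain the omission?**

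- Section 3.1: "All infants will receive PCV-10 per local standard of care". Infants of placebo mothers are therefore vaccinated like the others.
- Section 4.2, the added rule for objective 6: "infants who did not receive the PCV-10 vaccinations within the correct windows will be excluded". This does not remove infants by maternal arm.
- Section 5.3 uses the same two-vaccine wording for infants at week 8. There it fits, because primary objective 3 compares only the two vaccines.

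**3. How many infants are left out?** Section 3.1 plans 345 pairs, "equally distributed among three treatment arms to obtain" at least 100 evaluable pairs per arm. That is 345 / 3 = 115 enrolled per arm. Item vi covers about 2 × 100 = 200 of 300 evaluable infants.

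**4. What could be missed? (illustration)** The SAP gives no infant response rates, so the rates below are assumptions.

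- Model: 8 serotypes share one attainment rate p, with equicorrelated probit responses at correlation r. Given a standard normal z, q(z) = Φ[(Φ⁻¹(p) + √r·z) / √(1−r)], and P(at least 1 of 8) = 1 − E[(1−q(z))⁸].
- Test: chi-square without continuity correction, two-sided 0.05, 100 infants per arm. Power is by exact enumeration of both binomial counts.
- Both vaccine arms are given the same lowered rate.

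| Per-serotype attainment, placebo → both vaccine arms | At least 1 of 8, placebo vs vaccine, r = 0.3 | Same, r = 0.7 | Placebo-contrast power, r = 0.3 / 0.5 / 0.7 |
|---|---|---|---|
| 50% → 30% | 94.8% vs 81.3% | 80.6% vs 61.0% | 86.5% / 87.7% / 87.1% |
| 60% → 40% | 97.6% vs 89.8% | 87.5% vs 72.0% | 65.4% / 75.4% / 79.2% |
| 70% → 50% | 99.1% vs 94.8% | 92.7% vs 80.6% | 43.0% / 62.3% / 72.5% |
| 90% → 70% | 99.97% vs 99.1% | 98.9% vs 92.7% | 1.2% / 29.7% / 62.1% |

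In the first row the placebo differences are 94.8 − 81.3 = 13.5 points and 80.6 − 61.0 = 19.6 points. The PCV-10 versus PPV-23 difference is zero by construction, and a chi-square on it would reject about 5% of the time.

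**5. Item vii, if it were split by arm.** In all four rows the mean count falls by 8 × 0.20 = 1.6 serotypes. The variance of the count is 8p(1−p) + 56(π₁₁ − p²), where π₁₁ is the probability that two given serotypes both reach the cut-off. The largest standard error of the difference is 0.412 (60% → 40%, r = 0.7), so z = 1.6 / 0.412 = 3.88 and power is Φ(3.88 − 1.96) = 97%. This is the lowest of the four rows.

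**The case against.** The mismatch between item vi and objective 6 is not in dispute. The other side concerns its weight.

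- **Placebo infants are not absent from the plan.** Item vii includes them, the list in section 5.4 is not stated to be exhaustive, section 5 speaks generally of chi-square tests of vaccinated groups against placebo, and section 1 leaves table outlines to the Analysis Implementation Plan, which is not shown. This stands as mitigation but does not cure the gap. Item vii could be read as one pooled mean, a test against placebo cannot be run on a table with no placebo column, and a placebo column in the implementation plan would still go beyond item vi as worded.
- **It may be a carried-over phrase.** Item vi closely follows the week 8 infant wording of section 5.3. That is plausible, and it makes this a wording correction rather than a deliberate choice. The correction is still needed.
- **The power figures depend on assumed rates.** This stands. A 50% per-serotype rate in infants who have themselves received PCV-10 is a favourable case for the placebo contrast. For a fall from 95% to 90%, power on the at-least-one endpoint is below 2% at correlations 0.3 to 0.7. Adding placebo to item vi would then not reveal interference, which is a reason to specify item vii by arm as well.
- **Item vi specifies no test, and 100 per arm at week 24 is not guaranteed.** Both stand. Item vi plans proportions with confidence intervals, so the 5% rejection rate describes a test that the SAP does not name there. Exclusion of infants dosed outside the windows could bring numbers below 100 and lower the powers shown.

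**Conclusion.** The point holds. Item vi, followed as written, cannot answer the placebo part of secondary objective 6, and no design feature or population rule justifies dropping that arm. It omits about one third of the evaluable infants and two of the three contrasts. This conclusion rests on the text alone.

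The numerical consequence is illustrative. It assumes a common attainment rate across serotypes, equal correlation, an equal effect of both vaccines and 100 infants per arm. Across falls of 20 percentage points, placebo-contrast power runs from 1% to 88%, depending on the starting rate and the correlation. The point should be fixed, but it concerns one secondary objective and the primary analyses are unaffected. The unseen implementation plan may already contain the missing column.

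**What to change.** - **Item vi:** replace the restriction to infants of PCV-10 or PPV-23 mothers with *infants, by maternal Step 1 arm (PCV-10, PPV-23, placebo)*.
- **Item vii:** add *by maternal Step 1 arm*, and give differences in mean count with 95% CI for PCV-10 vs placebo, PPV-23 vs placebo and PCV-10 vs PPV-23. If the Analysis Implementation Plan already does this, a cross-reference is enough.
- **Optional:** because objective 6 names concentrations as its outcome measure, add geometric mean concentrations by arm at weeks 16 and 24, with ratios and 95% CI for the same contrasts. With 100 per arm and an assumed SD of 0.8 to 1.2 on the natural log scale, the CI limits are the ratio divided and multiplied by exp(1.96 × SD × √(2/100)), that is 1.25 to 1.39.

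The cost is one phrase in each of items vi and vii and a few more table columns from data already planned. No new samples or assays are needed.
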